Study Protocol

Study Protocol Number	MS202559_0001
Title	A study to investigate the association of real-world sensor-derived biometric data with clinical parameters and patient-reported outcomes for monitoring disease activity in patients with COPD
Protocol version identifier	3.0
Protocol Date/Version	01 MAR 2023 / 3.0
Replaces Version	Not applicable
Product reference	Not applicable. No medical device or medicinal product is investigated in this study.
Sponsor	Merck Healthcare KGaA an affiliate of Merck KGaA, Darmstadt, Germany [name]
Research question and objectives	
Primary Objectives:
 
1. To describe the distribution of sensor collected data on physical activity, heart rate, heart rate variability, temperature, respiration rate, cough frequency, and sleep pattern, by severity of COPD exacerbations.2. To predict moderate or severe COPD exacerbations by building a statistical model employing sensor-derived data and demographic and medical covariates. 
Secondary Objectives:
 
3. To evaluate the correlation of sensor collected data with
a) patients' self-assessed health status and symptoms (CAT) at baseline and study end,b) lung function and lab values at baseline and study end,c) and with history of mild, moderate and severe exacerbations at study end.4. Sensor derived data may be related to the CAT score, therefore, an additional objective is to investigate whether changes physical activity, heart rate, heart rate variability, temperature, respiration rate, cough frequency, and sleep pattern in the 3-month observation period, are associated with changes of the patient self-assessed symptoms (CAT).5. To predict the CAT score and changes thereof by building a statistical model employing sensor-

Company substance code **INN**
MS202559_0001

derived data and demographic and medical covariates.

Country(-ies) of study

Germany

Author

PPD [REDACTED], MD

Associate Director Clinical Research Bioelectronic
Merck Healthcare KGaA
[name]
[contact]

- Confidential -

3.1 Responsibilities of the Investigator

The Investigator is responsible for the conduct of the study at his/her site. He/She will ensure that the study is performed in accordance with the protocol and will ensure the quality and integrity of data, following all applicable international and national guidelines.

This study will not interfere with any treatment or any prescription by Investigators. Accordingly, the Investigator will decide in advance the best therapeutic strategy as well as monitoring of the underlying disease for each patient according to current practice, regardless of the potential participation of this patient in the study. Subsequently, the Investigator will consider the possibility of including the patient in the study.

The Investigator is responsible for adverse reaction and/or laboratory abnormalities recording and reporting, as specified in Section 11.

4 Abstract

Title	A study to investigate the association of real-world sensor-derived biometric data with clinical parameters and patient-reported outcomes for monitoring disease activity in patients
Rationale and background	
Remote patient monitoring (RPM) using wearable sensors has the potential to improve Chronic Obstructive Pulmonary Disease (COPD) patients' treatment and outcome by providing patients and physicians with early actionable insights, therefore reducing, or preventing exacerbations and increasing the quality of life. Previous published studies on sensor-based remote patient monitoring in patients with COPD suggest that such an approach is scientifically feasible and clinically promising, especially for decreasing the number of hospitalizations associated with exacerbations and improving overall outcome.
 
The purpose of this study (designated as "Sonstige Klinische Prüfung" (other clinical study) as per Art. 82 Regulation (EU) 2017/745 /§3 No. 4 MPDG) is to generate biometric sensor-derived data, correlate them to clinical parameters and patient reported outcomes and develop predictive models for COPD exacerbations and patients' disease status as a basis for a future RPM solution for patients with COPD.

Research question and objectives	
Primary Objectives:
 
1. To describe the distribution of sensor collected data on physical activity, heart rate, heart rate variability, temperature, respiration rate, cough frequency, and sleep pattern, by severity of COPD exacerbations.2. To predict moderate or severe COPD exacerbations by building a statistical model employing sensor-derived data and demographic and medical covariates. 
Secondary Objectives:
 
3. To evaluate the correlation of sensor collected data with a) patients' self-assessed health status and symptoms (CAT) at baseline and study end, b) lung function and lab values at baseline and study end, c) and with history of mild, moderate and severe exacerbations at study end.4. Sensor derived data may be related to the CAT score, therefore, an additional objective is to investigate whether changes in physical activity, heart rate, heart rate variability, temperature, respiration rate, cough frequency, and sleep pattern in the 3-month observation period, are associated with changes of the patient self-assessed symptoms (CAT).5. To predict the CAT score and changes thereof by building a statistical model employing sensor-derived data and demographic and medical covariates.

Study Design	
This multicenter, prospective cohort study will be conducted at 11 sites in Germany, a cohort of participants with COPD GOLD stage II-IV will be followed for 3 months.
 
During the Baseline visit each enrolled participant will be provided with a wearable device which records ECG, temperature and movement via an accelerometer and a connected smartphone and trained on the use of these devices. A study digital application is provided with the smartphone for the participants to fill in a daily COPD symptoms' questionnaire (CAT), label activities or events relevant for the interpretation of sensor signals, and receive notifications/reminders.
 
During the 3-month observation period the participants will attend visits at sites as per routine clinical practice in case of exacerbations or regular COPD check-ups. At all visits at the study sites, assessments will be performed as per physician's judgement and routine clinical practice.
 
At the end of the 3-month observation period, the participants will return the devices to the site during a regular COPD related visit scheduled at 3 months (\pm 14 days) after the baseline visit (Day 0). Additionally, a calibration cohort of non-COPD participants will be enrolled in an internal medicine center in Germany. The participants will use the wearable device during a 2-week observation period.

Population	
Key Inclusion criteria:
 
For participants with COPD:
 
 • Participants ≥ 40 and ≤ 80 years at baseline • Diagnosis of COPD stage II to IV (documented post-bronchodilator Forced Expiratory Volume in 1 second (FEV1)/ Forced Vital Capacity (FVC) < 0.7 and FEV1 $< 80\%$ predicted) • History of moderate or severe exacerbations (≥ 2 moderate exacerbations or ≥ 1 severe exacerbations in any 12-month time window during last 3 years prior to inclusion and ≥ 1 moderate or severe exacerbations in the last 12 months prior to inclusion, considering that the last 12 months may reflect lower exacerbation rate due to Covid-19 measures) 
For participants in the calibration cohort:
 
 • Participants ≥ 40 and ≤ 80 years at baseline 
Key Exclusion criteria:
 
For participants with COPD:
 
 • Participants with a cardiac pacemaker, defibrillators, or other implanted electronic devices • Participants with known allergies or sensitivity to silicon or hydrogel • Less than 6 weeks since previous moderate/severe exacerbation

	
For participants in the calibration cohort:
 
 • Participants with a cardiac pacemaker, defibrillators, or other implanted electronic devices • Participants with known allergies or sensitivity to silicon or hydrogel • Diagnosis of pulmonary disease including, but not limited to COPD, asthma, pulmonary fibrosis, with impact on the lung function and exercise capacity
Outcomes	
The primary outcome, COPD exacerbations during observation period will be defined as follows:
 
 • For moderate/severe exacerbation requiring a physician's intervention, emergency room visit or hospitalization, the severity, date of the exacerbation, and the duration of the exacerbation will be recorded via eCRF. • For mild exacerbations: self-reported; treated by the participant without intervention by a physician will be documented in the patient application labeling section (days with added treatment). 
Secondary outcomes will be defined as follows:
 
 • Patients' health status and symptoms at baseline (Day 0) and study end will be measured as the summary score across items of the CAT questionnaire that consists of 8-items in which participants can choose a score from 0 to 5, for each visit. • Lung function will be assessed using plethysmography and lab values including complete blood count (CBC) with differential, blood gas analyses (BGA), procalcitonin and CRP will be assessed as per standard practice at baseline (Day 0) and at study end. • Number, date of onset and duration of mild, moderate, and severe exacerbations, respectively, during the observation period. • During the observation period the CAT score will be obtained on a daily basis. Daily summary score across items of the CAT questionnaire will be computed. • Patients' health status and symptoms at baseline (Day 0) will be measured as the summary score across items of the CAT questionnaire that consists of 8-items in which participants can choose a score from 0 to 5. During the observation period the CAT score will be obtained via a digital application on a daily basis.
Key Variables	
Variables measured with the Vivalink wearable device (including, but not limited to):
 
 • Physical activity • Heart rate • Temperature • Respiration rate 
Self-measured Variables:
 
 • Data on Self-reported COPD symptoms will be collected via the CAT questionnaires using the participant app

	
 Self-reported activities (e.g., coughing, sports, sleeping) as collected by the participant app Self-reported satisfaction to the study, collected via end of study questionnaire 
Covariates will be collected from patient records (status at the time of Day 0, closest record prior to):
 
 Demographics, Body mass index, Smoking status Relevant medical history, comorbidities, current medication including COPD treatment at baseline Date of diagnosis of COPD and COPD severity (GOLD stage) Number of moderate or severe exacerbations prior to baseline visit (at Day 0, moderate/severe exacerbation visit and End of study visit): Current body plethysmography parameters Current (capillary) pO₂, O₂ saturation and pCO₂ 
Several biomarkers at the time of baseline depending on availability

Data Sources	
The data source used for this study will consist of patients charts from 11 sites (mainly pulmonology private practices) in Germany as well as from a device, which will get handed out to the participant.
 
The data informing this study will be extracted from patient medical records using eCRF directly in an electronic data capture system. In addition, a patient reported outcomes (PRO) questionnaire (COPD assessment tool [CAT], filled in by the participant electronically), and a wearable device (adhesive patch device with sensors) will be used for data collection.

Study Size	
Sample size required to show a sensitivity of ≥ 0.85 for a model predicting moderate to severe COPD exacerbations was estimated to be 67 participants including a drop-out rate of 10%. The study will also observe 10 participants in the calibration cohort for 2 weeks. The number of participants for this cohort is chosen on an exploratory basis.

Data Analysis	
Sensor collected data on physical activity, heart rate, heart rate variability, temperature, respiration rate, cough frequency, sleep pattern, at baseline, and shortly prior (14 days prior to, 7 days prior) to, during an exacerbation and after an exacerbation (8 to 14 days after, 2 weeks after, 3 weeks after, up to 4 weeks after an exacerbation) will be reported as mean (SD) and/or median (Interquartile Range) for continuous variables and counts and frequency (%) for categorical variables.
 
A statistical model employing sensor collected data to predict COPD exacerbations will be built as follows:
 
As input to the model a number of algorithms (e.g. self-learning algorithms) for obtaining derived parameters such as cough frequency, physical activities and sleep pattern will be developed first using the label dataset obtained via the app.

Company substance code **INN**
MS202559_0001

	Different machine learning algorithms will be evaluated, and their performance will be assessed by estimating their accuracy, specificity, sensitivity, and area under ROC metrics.
--	---

5 Amendments and Updates

The following amendments and updates to the protocol were implemented.

Protocol Number	Date	Section of Study Protocol	Amendment or update	Reason
3.0	01 MAR 2023	throughout	Changed the number of study centers from "up to 10" to "11".	To achieve enrolment more than anticipated study centers need to be activated.
2.0	21 OCT 2022	9.2.1	Added capability of giving signed informed consent to in-/exclusion criteria.	EC request
		9.2.4	"Data collection via App (labeling events and activities)" added to Table 5: Planned Assessments Calibration Cohort	Correction of oversight.
		9.10.1	Addition of Section 9.10.1 Ethical Conduct of the Study	EC request to add a statement of compliance
		9.10.6	Addition of Section 9.10.6 Medical Device Supply, Accountability and Handling	EC request to add a description on the accountability of the device.
		10.1	Deleted possibility to delegate patient informed consent taking	EC request to clarify that informed consent is given exclusively by investigators.
		throughout	Correction of typos and spelling of units	Correction of oversights.

6 Milestones

Not applicable as no existing databases are used.

7 Rationale and Background

Chronic Obstructive Pulmonary Disease (COPD) is a progressive life-threatening lung disease with no curative treatment available (Christenson 2022). According to the World Health Organization (WHO), COPD is currently the fourth, and will soon become the third, most frequent cause of death worldwide (WHO 2022; Quaderi 2018). It is also associated with high costs for treating and managing patients (Sullivan 2000). The Global Burden of Disease Study reports a prevalence of 251 million cases of COPD globally in 2016.

COPD exacerbations are defined as an acute worsening of respiratory symptoms that result in additional therapy (GOLD 2022). Exacerbations usually cause further damage to the lungs, lead to more rapid progression, and carry a substantial mortality risk (Rhodes 2022). Hence, frequency of exacerbations is an important efficacy endpoint in COPD clinical studies and pharmacological therapy of COPD is used to reduce frequency and severity of exacerbations. Exacerbations are classified by severity into severe, moderate and mild. The Global Initiative for Chronic Obstructive Lung Disease (GOLD) consortium defines these as severe if they require hospitalization, moderate if they require added drug treatment from the group of systemic corticosteroids and antibiotics which requires a physician's interaction, and mild if they can be treated by the patient by an additional (inhaled) drug without intervention of a physician (Vogelmeier 2017). The main target

of all therapeutic approaches are the severe and moderate exacerbations. Limited knowledge exists on the importance of mild exacerbations.

Most patients with COPD experience chronic respiratory symptoms and limitations to their daily lives such as chest tightness and shortness of breath, chronic cough and excessive mucus, activity and exercise limitations and impaired physical functioning (Kessler 2011; Landis 2014). The COPD Assessment Test (CAT) was developed according to the Food and Drug Administration's (FDA) patient reported outcome development guidance, and it is a short digital or paper tool that can be used to assess the symptoms of COPD (Jones 2013).

Since its launch in 2009, CAT has been used globally, with >90 approved and linguistically validated translations. Furthermore, clinical and observational studies, as well as randomized controlled trials, have used CAT as a measure of health-related quality of life (HRQoL) and clinical efficacy, respectively (Müllerová 2019).

The CAT has also been incorporated in the GOLD combined assessment to establish a threshold at which patients become symptomatic to justify and guide in the selection of treatment (Jones 2013) and is used in routine clinical practice. The score is higher in people with more frequent exacerbation and it changes with the onset and recovery from an exacerbation (Al Rajeh 2020, Zimmermann 2020). The 8 items of the CAT questionnaire provide a scoring range of 0 to 40. A 2-point change in the CAT score has been established as the Minimally Clinically Important Difference (MCID, Kon 2014). Importantly, the CAT closely reflects the functional status of patients with COPD (Gulart 2017).

Remote patient monitoring using wearable sensors has the potential to improve treatment and outcomes of patients with COPD by providing patients and physicians with early actionable insights, therefore reducing, or preventing exacerbations and increasing the quality of life. Previous published studies on sensor-based remote patient monitoring in patients with COPD suggest that such an approach is scientifically feasible and clinically promising, especially for decreasing the number of hospitalizations associated with exacerbations and improving overall outcome (Pedone 2013; McLean 2011; Isaranuwatchai 2018).

The purpose of this study (designated as “Sonstige Klinische Prüfung” [other clinical study] as per Art. 82 Regulation [EU] 2017/745 /§3 No. 4 Medizinproduktgerecht-Durchführungsgegesetz [MPDG]) is to generate biometric sensor-derived data, evaluate their correlation to clinical parameters and patient reported outcomes (PRO) and develop a predictive model for COPD exacerbations as well as for monitoring current disease status and changes thereof. In the this study the participants will receive a wearable device (Vivalink) with sensors that will measure heart rate, heart rate variability, respiration patterns, temperature, and physical activity. The analysis of this data will help to understand the utility of remote patient monitoring using a multimodal sensor approach and contribute to the development of a future remote patient monitoring solution. The purpose of this study is not to evaluate, validate, nor register the device itself, the device merely serves as a means for collecting the targeted sensor-derived data.

Specifically, this study aims at predicting 2 target outcomes: acute exacerbations of COPD (AECOPDs) as defined by the GOLD initiative, and the CAT score as a proxy for patients' disease status. The start of an exacerbation within a patient, regardless of how many exacerbations the patient may have experienced before, will be predicted based on sensor data preceding the

exacerbation, and using basic covariates as well. For type of exacerbations, the severe and moderate exacerbations are considered as our main target as these are linked to the need of urgent medical intervention and will predict those as a group, but also separately (distinguish by type), if possible. Mild exacerbations, the relevance of which is currently a subject of investigation in the field, will also be explored.

For the CAT score, the aim is to predict the total score (max = 40) from the sensor data, and changes in the CAT score of ≥ 2 based on the MCID. With this approach, it is aimed to use the model built on sensor data as an objective means to reflect patients' disease status. While for the prediction of exacerbations the aim is to predict them as early as possible, i.e. days before an exacerbation, for the CAT/disease status prediction the aim is to reflect the daily status.

CCI

This study is exploratory in nature and any predictive models will need to be validated in future studies. A future remote patient monitoring (RPM) solution for patients with COPD built on these models will have 2 prime utilities: First, ameliorating or preventing exacerbations and their negative sequelae by early treatment intervention and second, to provide physicians and patients with a highly granular and precise view on the current disease status and past changes. Such information can be used by the treating physician to optimize therapeutic regimens and by the patients to accompany and optimize lifestyle changes. By using a multimodal sensor approach we intend to increase the accuracy of our predictive models beyond what has been described in the literature and thereby increase their clinical utility.

8 Research Question and Objectives

The aim of the study is to investigate the correlation of real-world sensor-derived biometric data obtained via a wearable device with clinical parameters and PROs for monitoring disease activity and predicting exacerbations for patients with COPD.

Participants with COPD and participants in the calibration cohort will receive a wearable device to measure physiological parameters during normal daily activities and sleep and will use a digital application to daily record symptoms, events, and/or activities. The sensor-collected data will be statistically explored, and algorithms derived for a.) predicting exacerbations b.) assessing the health status and changes in the health status of the participant.

[figure not shown]

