9.5 Study Size

Sample size calculation is based on the second part of the primary objective, especially on predicting exacerbations of a severe or moderate type as outcome.

Assuming a desirable sensitivity and specificity of 0.85 for our algorithm and requiring that the lower 95% confidence limit should be at least 0.50 (with a probability of 0.95) for this exploratory approach, the number of observed exacerbation events needed is 18 ([Flahault 2005](#)).

Assuming that patients with COPD within our eligibility criteria (GOLD stage II-IV with a history of at least 2 moderate and/or severe exacerbations within any 12 month period within the last 3 years and at least 1 moderate or severe exacerbation within the last 12 months) show a frequency of 2 moderate or severe exacerbations per year, participants with COPD will have 0.5 events in 3 months (the in-study time). Further assuming that event occurrence over 3 months for every individual participant follows a Poisson distribution with parameter $\lambda = 0.5$, the number of events in the overall study population is also Poisson distributed and the corresponding parameter is the sum of individual parameters λ . Calculations show that a λ of 30 is needed to reach an upper cumulative distribution probability of 0.99 for observing at least 18 exacerbations. Therefore, 60 participants are needed to observe at least 18 exacerbation events within the 3-month observation period.

The events of interest in the context of the present study are COPD exacerbations (severe or moderate), exactly the onset of an exacerbation. For building the binary classifier predictive models we also require “no exacerbation” events. We will sample such events randomly from periods with no exacerbations, avoiding 2 weeks before and after an exacerbation.

Considering a drop-out rate of 10%, the estimated number is 67 participants with COPD that need to be included in this study.

This recruitment number is also in good agreement with published studies with regards to the ability to build predictive models for exacerbations. Studies with similar recruitment numbers ([Yañez 2012](#)) have been able to predict exacerbations based on single parameters studied. Strong features can compensate for low numbers in COPD machine learning model building as shown in

[Al Rajeh 2020](#), and using several features improves the accuracy of predictive models as seen in [Jensen 2012](#).

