### 1.3.2 Study size

Sample size calculation is based on the second part of the primary objective, especially on predicting exacerbations of a severe or moderate type as outcome.

Assuming a desirable sensitivity and specificity of 0.85 for our algorithm and requiring that the lower 95% confidence limit should be at least 0.50 (with a probability of 0.95) for this exploratory approach, the number of observed exacerbation events needed is 18 (1).

Assuming that COPD patients within our eligibility criteria (GOLD stage II-IV with a history of at least 2 moderate to severe exacerbations within any 12 month period within the last 3 years and at least 1 exacerbation within the last 12 months) show a frequency of 2 moderate or severe exacerbations per year, COPD participants will have 0.5 events in 3 months (the in-study time). Further assuming that event occurrence over 3 months for every individual participant follows a Poisson distribution with parameter  $\lambda = 0.5$ , the number of events in the overall study population is also Poisson distributed and the corresponding parameter is the sum of individual parameters  $\lambda$ . Calculations show that a  $\lambda$  of 30 is needed to reach an upper cumulative distribution probability of 0.99 for observing at least 18 exacerbations. Therefore, 60 participants are needed to observe at least 18 exacerbation events within the 3-month observation period.

The events of interest in the context of the present study are COPD exacerbations (severe or moderate), exactly the onset of an exacerbation. For building the binary classifier predictive models we also require “no exacerbation” events. We will sample such events randomly from periods with no exacerbations, avoiding 2 weeks before and after an exacerbation.

Considering a drop-out rate of 10%, the estimated number is 67 COPD participants that need to be included in this study.

This recruitment number is also in good agreement with published studies with regards to the ability to build predictive models for exacerbations. Studies with similar recruitment numbers (2) have been able to predict exacerbations based on single parameters studied. Strong features can compensate for low numbers in COPD machine learning model building as shown in (3), and using several features improves the accuracy of predictive models as seen in Jensen 2012.

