Different machine learning algorithms will be evaluated, and their performance will be assessed by estimating their accuracy, specificity, sensitivity, and area under ROC metrics. Other usual evaluation metrics such as precision, positive predictive value (PPV), negative predictive value (NPV), F1-score will be computed.

This analysis will be performed on the COPD cohort. Internal cross-validation will be tested.

The following models will be used:

- Logistic regression
- Random Forest
- K-nearest neighbors
- Boosting methods (e.g., Gradient boosting machine, GBM)
- Support vector machines (SVM)

Other methods may be tested.

The development of those models will be based on the machine learning algorithms implementation of scikit-learn (12), a python package designed for predictive data analysis. Other packages may be considered if needed (e.g., H2O (13)).

To optimize the performance of the models, feature extraction and selection algorithms will be used.

Explanatory models will be built on top of the selected machine learning algorithm (14), as a way to support rationalization for physicians and regulatory organizations. Depending on the selected ML model selected, either model specific (for logistic regression, decision trees, k-nearest neighbors) or model agnostic methods will be considered (global methods as PDP, ALE, functional decomposition, and local methods as LIME and Shapley values).

### 3.4.5.3 Secondary Objective 3

Objective 3 will be analyzed on the COPD cohort. For each pair of variables and outcomes ( $x, y$ ) defined below, Pearson's correlation coefficient will be computed together with a 95% asymptotic confidence interval based on Fisher's Z transform.

In case of low variability in parameter values (e.g., exacerbation count), parameters may be treated as ordinal and analyzed in terms of Kendall's Tau statistic with non-parametric confidence interval (see (15)).

The following variable groups and outcomes will be paired and assessed at the indicated time points:

Group x	Group y	Time points for assessment
Sensor data (see section 2.1.4), daily averages (17 variables): physical activity, heart rate, resting heart rate, heart rate variability, temperature, respiration rate, ratio of in- vs expiration time, cough frequency, sleep pattern (hours of sleep)	CAT summary score: Self-assessed patient's health status by CAT questionnaire.	Baseline (Day 0), End of study visit

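### The abstract says 67 participants are needed to show sensitivity of at least 0.85, but the study is sized only for a lower 95% limit of at least 0.50 if sensitivity is 0.85

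*Protocol*

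**What the plan says.** The Study Size entry in the abstract (Protocol Section 4) begins "Sample size required to show a sensitivity of ≥ 0.85 for a model predicting" moderate to severe exacerbations, and says that this size "was estimated to be 67 participants including a drop-out rate of 10" percent. It mentions no confidence limit, no specificity and no event count. It uses the word exploratory only for the calibration cohort.

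Protocol Section 9.5 gives the derivation. It starts from "Assuming a desirable sensitivity and specificity of 0.85 for our algorithm" and goes on to "requiring that the lower 95% confidence limit should be at least 0.50 (with a probability of 0.95) for this exploratory approach". This leads to 18 events. With 0.5 events expected per participant in three months, the section concludes: "Therefore, 60 participants are needed to observe at least 18 exacerbation events within the 3-month observation period". Allowing for 10% drop-out gives 67. SAP Section 1.3.2 uses the same criterion: "Assuming a desirable sensitivity and specificity of 0.85 for our algorithm and requiring that the lower 95% confidence limit should be at least 0.50".

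For primary objective 2, SAP Section 3.4.5.2 says of the algorithms that "their performance will be assessed by estimating their accuracy, specificity, sensitivity, and area under ROC metrics", and adds: "Other usual evaluation metrics such as precision, positive predictive value (PPV), negative predictive value (NPV), F1-score will be computed". No confidence limit is listed for any of these measures.

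**The concern.** In the abstract, 0.85 is the value to be shown. In the derivation, 0.85 is the value assumed to be true, and 0.50 is the value that the lower limit has to reach. These are different claims about primary objective 2, attached to the same 67 participants. A reader who relies on the abstract would expect evidence that the design was not built to give.

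There is a related gap in the outputs. The study is sized on a lower confidence limit, but the SAP does not list that limit among the results for this objective, although Section 3.4.5.3 plans 95% confidence intervals for the correlations in objective 3. The planned outputs would not show directly whether the intended precision was reached.

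**Working it through.** **Inputs** (Protocol Section 9.5, repeated in SAP Section 1.3.2): assumed sensitivity 0.85; lower 95% limit at least 0.50 with probability 0.95; 2 exacerbations per year, so 0.5 in three months; probability 0.99 of reaching the event count; 10% drop-out. Neither section says whether the limit is one- or two-sided, so both were tried with exact (Clopper-Pearson) limits.

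**1. The 18 events.** The one-sided exact lower limit for x detected out of n is at least 0.50 when P(X ≥ x | n, 0.50) ≤ 0.05.

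- n = 18: P(X ≥ 13 | 18, 0.50) = 0.048, while 12 of 18 gives a lower limit of only 0.446. At least 13 must be detected. P(X ≥ 13 | 18, 0.85) = 0.958, which meets 0.95.
- n = 17: 13 are again needed, and P(X ≥ 13 | 17, 0.85) = 0.901, which falls short.

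So 18 is the smallest number of events that meets the criterion, as the plan states.

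**2. The 60 and 67 participants.** 60 × 0.5 = 30 expected events. Poisson P(X ≥ 18 | mean 30) = 0.993, above 0.99. Then 60 / 0.9 = 66.7, rounded up to 67. Both figures reproduce.

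**3. What 18 events can show.**

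| Detected | Observed sensitivity | One-sided 95% lower limit |
|---|---|---|
| 13/18 | 0.72 | 0.502 |
| 16/18 | 0.89 | 0.690 |
| 17/18 | 0.94 | 0.762 |
| 18/18 | 1.00 | 0.847 |

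The last row is 0.05^(1/18) = 0.847; with a two-sided limit it is 0.025^(1/18) = 0.815. The sizing criterion is met with an observed sensitivity well below 0.85, and no result from 18 events puts the lower limit at 0.85 or above.

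**4. If the limit were two-sided.** With 2.5% in the lower tail, 18 events need 14 detected, and P(X ≥ 14 | 18, 0.85) = 0.879. The smallest number of events that meets 0.95 is 23 (17 needed, probability 0.954). A mean of 30 delivers at least 23 events with probability 0.919, against the 0.99 that Section 9.5 asks for. With exact limits, then, 18 follows only from the one-sided reading.

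**5. Specificity.** The 18 exacerbations fix the precision of sensitivity only. The precision of specificity depends on how many non-exacerbation time points are sampled. Protocol Section 9.5 and SAP Section 2.3.1 describe that sampling but give no number.

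**The case against.** The strongest reply is that this is one condensed sentence in an abstract. The operative text in Section 9.5 and SAP Section 1.3.2 is consistent, Section 9.10.3 monitors the same target of 18 events, and no decision rule in the visible text uses a sensitivity of 0.85. Protocol Section 7 calls the study exploratory and leaves validation to later studies, and Section 9.9 says the number of exacerbations will be low. All of this is correct and it limits the consequence. It does not remove the contradiction, because the abstract attaches the claim directly to the sample size for primary objective 2.

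A reader might go further and infer that 67 is too few. At the expected 30 events and a true sensitivity of 0.85, the one-sided lower limit reaches 0.85 with probability only about 0.05, and the observed value reaches 0.85 about half the time. These figures are not evidence of a shortfall. When the truth is exactly 0.85, they come out much the same at almost any sample size: at 1,000 events the first is still 0.049 and the second 0.52. The documents also give no true value above 0.85 from which a larger sample could be derived.

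On sidedness, a lower 95% limit can fairly be read as one-sided, and that reading reproduces 18. The point is therefore a clarification and does not show that 18 is wrong.

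It may also be said that the missing confidence limit in the SAP is a separate matter. It does not follow from the abstract's wording, but it concerns the quantity on which the study was sized and is cheap to add. One caution holds: several algorithms and feature selection are planned, so a limit computed on the selected model's apparent performance would be optimistic.

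**Conclusion.** The abstract is wrong as written. It turns an assumed sensitivity into one to be demonstrated, and leaves out both the 0.50 limit and specificity. The figures 18, 60 and 67 are right for the criterion in Section 9.5, read with a one-sided exact limit. The size of the discrepancy is the distance between the two claims: at the target event count an observed 0.72 satisfies the sizing criterion, while even perfect detection leaves the lower limit at 0.847.

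This takes showing a sensitivity of at least 0.85 to mean a lower confidence limit at or above 0.85; the abstract does not define the term. It also treats the events as independent, as a simple binomial calculation does. The documents do not support the stronger conclusion that enrolment must rise. The correction should be made, but it concerns the claim and the reporting only.

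**What to change.** 1. **Protocol abstract, Study Size.** Replace the claim with wording such as: *67 enrolled (60 evaluable) gives about 0.99 probability of observing at least 18 moderate or severe exacerbations under the assumed rate; if true sensitivity is 0.85, 18 events give at least 0.95 probability that the one-sided lower 95% confidence limit for sensitivity is at least 0.50; the study is exploratory and is not sized to show sensitivity ≥ 0.85.* Do not extend this sentence to specificity unless the number of sampled non-exacerbation events is also stated.
2. **Protocol Section 9.5 and SAP Section 1.3.2.** State that the limit is one-sided. If the authors intended a two-sided limit, restate the 0.95 as about 0.88 at 18 events, and acknowledge that 23 events would be needed and that a mean of 30 reaches 23 with probability about 0.92.
3. **SAP Section 3.4.5.2.** Add the lower 95% confidence limit for sensitivity, and likewise for specificity, computed from cross-validated predictions and with the sidedness stated in item 2.

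The cost is one abstract sentence, one clarification in each study-size section and two extra reported limits. Participants, visits and the target of 18 events stay as they are. The abstract's claim becomes more modest.
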